****Updated to add changes in inclusionary criteria**

****Updated July 15, 2025 – Includes statistical analysis plan.**

Human Subjects Involvement, Characteristics, and Design

The study is a Phase I clinical trial that employs a randomized parallel design. We plan to enroll 160 children diagnosed with Developmental Language Disorder and their caregivers who will provide services to approximately half of these children. We predict that 15% of the children (N=20) will be lost to follow-up, thus we enroll 160, in order to have 140 children complete the entire study and meet the planned enrollment goals. Children will be randomly assigned to one of four treatment conditions, thus we expect 35 participants per condition. Research will be carried out at the University of Delaware and the University of Maryland College Park.

Children with Developmental Language Disorder (N = 160)

Inclusionary & Exclusionary Criteria:

- Age: 4-7 years old
- Primarily English speaking: Less than 20% exposure to another language, per parent report
- Document poor syntax skills: standard score below 85 on the DELV-NR composite, a dialect neutral assessment (Seymour, Roeper, de Villiers, & De Villiers, 2005).
- Nonverbal IQ within typical range: t-score at or above 35 on the DAS, matrices subscale, (Elliott, 2007).
- Hearing within the typical range: Pass screening using SoundScouts (Gumbie et al., 2018; Mealings et al., 2020) or provide reports of passing a hearing screening at school or in a pediatrician's office. *Due to COVID and limitations on in person activities, treatment may proceed even if these reports are not obtained if no one has concerns about hearing and we will track/follow up with families to obtain a clear hearing screening within 12 months of completion of intervention. Documentation of how many children did not complete hearing screenings will be retained and inform interpretation of data.
- No diagnosis of Autism: Cutoff score of 15 on the SCQ, (Rutter, Bailey, & Lord, 2003)
- No diagnosis of significant sensory-motor concerns or significant psychiatric disorders per parent report
- Able to benefit from treatment:
 - Score below 60% correct on experimenter developed elicited production probes of passives and object relative clauses
 - Producing simple transitive sentences (SVO) and MLU of 2.5 on 100 utterance language sample

Caregivers of Children with DLD (N=160)

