A single caregiver will be identified at the time of enrollment to receive training in study procedures. In general, the caregiver's race will align with the child's race. Overwhelmingly women are the caregiver who coordinate this type of care, bring children to appointments, and engage in parent provided treatment. That said, we do not restrict this role to parents or to women. We will take care with our materials to encourage the participation of any primary caregiver.

Inclusionary & Exclusionary Criteria:

- Basic literacy skills per self-report
- Willing to participate in caregiver training and caregiver-based treatments if child is assigned to that condition
- Willing to participate in questionnaires and structured interviews during post-test

Study Procedures, Materials, and Potential Risks

Materials.

Screening and pre- and post-test materials will consist of commercially available standardized tests (see inclusionary and exclusionary criteria above) and experimenter developed probes. The experimenter developed probes will utilize illustrations that are child friendly to support the elicitation and comprehension of passives and object relative clauses.

Screening

After providing informed consent, parents will complete a case history form, the FOCUS questionnaire, the SCQ, and the BRIEF. An SLP or research associate will administer standardized and non-standardized assessments, including the DAS-2, matrices subscale, the DELV, the PPVT-5, the EVT-3, and a language sample. All information obtained will be coded with an alphanumeric code to protect confidentiality and stored on secure university servers. A 10-item elicited production probe will be completed at this point to determine if the child may advance to the pre-test stage.

Pre- & Post-Test

Children who qualify as DLD will be administered 2 20-item production probes to elicit passives and relative clauses. They will participate in a hearing screening. They will complete 2 blocks of 24-item comprehension probes (48 items total) to assess online comprehension of active/passive and object/subject relative clauses using a 2AFC eye tracking task administered via PClbex. Additional language sample data will be collected to ensure sufficiently large samples for analysis. Audio files, transcription, visual fixation data, and scoring will be coded with an alphanumeric code to protect confidentiality and stored on secure university servers.

Treatment

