$$\begin{aligned} \text{Likelihood of a Correct Production} &= \text{TestPoint} * \text{TreatmentCondition} * \text{EstimatedDose} \\ &\quad + (1|\text{item}) + (\text{clause type} |\text{subject}) \\ \text{Structural Sensitivity} &= \text{TestPoint} * \text{TreatmentCondition} * \text{EstimatedDose} \\ &\quad + (\text{clause type} |\text{subject}) \end{aligned}$$

In the event that the interaction between time point and treatment is not significant, we can directly test for treatment efficacy by comparing the effect of treatment on the treated or untreated structures. We expect that the model estimate for Treated vs. Untreated clause will be significant at p<0.05 level, favoring the treated clauses, demonstrating that treatment was effective and ruling out maturational effects.

$$\begin{aligned} \text{Likelihood of a Correct Production} &= \text{TestPoint} * \text{TreatedOrUntreated} \\ &\quad + (1|\text{item}) + (\text{clause type} |\text{subject}) \\ \text{Structural Sensitivity} &= \text{TestPoint} * \text{TreatedOrUntreated} \\ &\quad + (\text{clause type} |\text{subject}) \end{aligned}$$

Power Analysis for Production

Power analyses were carried out using Monte Carlo simulation (5,000 iterations) via SAS 9.4 and PROC GLIMMIX using residual pseudolikelihood estimation of a binary logistic mixed effects model with item responses (n=20) nested within tests (n=4 representing test point and clause type repeated measures) that are nested within children (n=120) who have been randomly assigned to treatment conditions, counterbalanced across the 2 clauses. Random effects are included for items within clauses, as well as four correlated child-level random effects (i.e., for each of the four repeated measures). A single model was used to estimate power in alignment with the overall design of the study in which children are randomly assigned to one of FOUR conditions. Power for the more focused models described above can be inferred from the power estimates for the treatment contrasts below. By adopting this randomization scheme and model design, we retain the ability to test unplanned contrasts that go beyond the planned analyses for the Aims if we so chose (e.g., recasts in the lab vs. recasts at home) in order to carry out secondary analysis associated with cost effectiveness, dose, or home environment.

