Test scores were simulated based on means and standard deviations of pretest and posttest scores from a previous study. Pretest scores for both clauses were sampled from a Normal distribution with $M=3.0$ and $SD=2.5$, rounding to the nearest integer, with a minimum score of 0 and maximum score of 7 items correct (corresponding to the >40% correct study eligibility criteria). Posttest scores for untreated clauses were sampled from a Normal distribution with a correlation of .90 with pretest scores and $M=3.0$ and $SD=2.5$, rounding to the nearest integer, with a minimum score of 0. Posttest scores for treated clauses were sampled from a Normal distribution with a correlation of .90 with pretest scores, rounding to the nearest integer, with a minimum score of 0, and $M=5.5$ and $SD=4.0$ for the syntax stories at home condition ($ES=+1.0$), $M=4.0$ and $SD=4.0$ for the parent recasts condition ($ES=+0.4$), $M=6.0$ and $SD=3.5$ for the syntax stories in the lab condition ($ES=+1.2$), and $M=8.0$ and $SD=3.5$ for the lab recasts condition ($ES=+2.0$).

Based on the above effect size estimates, power for detecting main effects in Aim 1 exceeds .95 for the syntax stories at home, syntax stories in the lab, and lab recasts. Power is .61 for detecting main effects of parent recasts (i.e., the effect of parent recasts would need to exceed .50 to be detected with 80% power). Power for treatment effect contrasts is .75 to detect differences in syntax stories at home and parent recasts effects, .90 to detect differences in parent recasts and syntax stories in the lab effects, and .99 to detect differences in parent recasts and lab recasts effects. Other contrasts (e.g., syntax stories at home vs. syntax stories in the lab) have power less than 80% if the expected effect sizes hold true (i.e., +1.0 vs. +1.2); differences in effects would need to exceed 0.35 logits (2 raw score points) in order reach statistical significance with 80% power.

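### The production power simulation caps pre-test scores for a 40% entry rule, but the eligibility criteria say below 60%, so the stated powers rest on an entry rule other than the one in the criteria

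*Protocol*

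**What the plan says.** - **Entry rule** (Protocol, Inclusionary & Exclusionary Criteria for children): "Score below 60% correct on experimenter developed elicited production probes of passives and object relative clauses".
- **How entry is tested** (Protocol, Screening): "A 10-item elicited production probe will be completed at this point to determine if the child may advance to the pre-test stage".
- **Baseline for the outcome** (Protocol, Pre- & Post-Test): "Children who qualify as DLD will be administered 2 20-item production probes to elicit passives and relative clauses".
- **Simulation structure** (Protocol, Power Analysis for Production): "item responses (n=20) nested within tests (n=4 representing test point and clause type repeated measures", with 120 children in four conditions.
- **Simulated pre-test** (same section): Normal with mean 3.0 and SD 2.5, rounded, at least 0, and a "maximum score of 7 items correct (corresponding to the >40% correct study eligibility criteria". Post-test scores have a "correlation of .90 with pretest scores".
- **Results given there:** power above .95 for three main effects and .61 for parent recasts. The contrasts of parent recasts with stories at home, stories in the lab and lab recasts have power .75, .90 and .99. A difference of 0.35 logits, equated with 2 raw points, is detectable at 80% power. The Aim 1 text repeats the .35 and 2-point figures.

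**The concern.** The power section says its cap follows from eligibility, but the criterion it names is not in the eligibility list. Both statements are current text. The document's header notes a change to the inclusion criteria, which may explain the mismatch, but the protocol does not say so.

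The stated powers and the detectable difference all come from this simulation, and the eye-tracking section takes its sample size (n=120) from it. Two of the powers, .61 and .75, are already below .80. Baseline level also matters for a logit outcome. Two raw points from 3 to 5 of 20 is ln(5/15) − ln(3/17) = 0.64 logits, while from 9 to 11 of 20 it is ln(11/9) − ln(9/11) = 0.40. A raw-point figure worked out for pre-tests of 0 to 7 need not carry over to children who start at 8 to 11.

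**Working it through.** **1. The ceilings.** With 20 items per probe, 7/20 = 35%. Below 40% means fewer than 8 items, so at most 7. Below 60% means fewer than 12 items, so at most 11 (55%). On the 10-item screen, below 60% means at most 5.

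**2. Can the wording be reconciled?** Taken literally, more than 40% correct would admit only scores of 9 or more, the opposite of a cap at 7. Read as more than 40% incorrect, it matches below 60% correct, but the cap would then be 11. Neither reading gives both 60% and a cap of 7.

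**3. The plan's own figures.** Effect size = (post-test mean − 3.0)/2.5:
- stories at home: (5.5 − 3.0)/2.5 = 1.0
- parent recasts: (4.0 − 3.0)/2.5 = 0.4
- stories in the lab: (6.0 − 3.0)/2.5 = 1.2
- lab recasts: (8.0 − 3.0)/2.5 = 2.0

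All four match the protocol. The powers could not be reproduced together. The table uses 30 per arm, two-sided alpha .05, and out-of-range scores set to the limit. The mixed model used 250 runs (Monte Carlo SE about .03) and the raw-gain t-tests 3,000. PR = parent recasts, SH = stories at home, SL = stories in lab, LR = lab recasts.

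| | PR main | SH vs PR | PR vs SL | PR vs LR |
|---|---|---|---|---|
| Protocol | .61 | .75 | .90 | .99 |
| Mixed model, cap 7 | .62 | .50 | .77 | 1.00 |
| Mixed model, cap 11 | .70 | .48 | .79 | 1.00 |
| Raw gain, cap 7 | .83 | .70 | .93 | 1.00 |
| Raw gain, cap 11 | .86 | .74 | .95 | 1.00 |

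The protocol does not give the item variance, the between-clause correlation or the exact contrasts, so the mismatch is not evidence that its powers are wrong.

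**4. Changing only the cap.** P(score above 7) = P(Z > (7.5 − 3.0)/2.5) = P(Z > 1.8) = .036. If out-of-range scores are set to the limit, moving the cap from 7 to 11 takes the mean from 3.08 to 3.14 and the SD from 2.15 to 2.28. If they are redrawn, the mean goes from 3.20 to 3.41 and the SD from 1.93 to 2.16. The protocol does not say which was done. Power in the table moves by −.02 to +.08, partly Monte Carlo error.

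**5. Changing the distribution as well (assumptions, not in the protocol).** Cap 11, pre-test mean 5 or 7 of 20, mixed model:

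| | PR main | SH vs PR |
|---|---|---|
| Cap 7, mean 3 | .62 | .50 |
| Mean 5 / 7, same raw gains | .29 / .21 | .52 / .41 |
| Mean 5 / 7, same logit gains | .67 / .71 | .69 / .76 |

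Power falls or rises according to which gain is held fixed.

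**The case against.** The strongest reply is that this is a wording slip with little effect. The simulated means and SDs come from a previous study. If that distribution still describes the children enrolled, only about 4% of pre-tests lie above 7 and power hardly changes. This stands, and it limits the point. It does not show that a mean of 3.0 fits children admitted up to 60%, on which the protocol gives no data.

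A second reply is that the simulation uses 120 children (30 per condition) while the design section expects 35 per condition to complete. At 35 per arm, cap 7, the mixed model gives .73, .56, .83 and 1.00 for the four effects in the order tabulated. That margin could offset some loss, but it does not make the stated basis correct.

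In the other direction, a reader might infer that the powers are overstated, because higher scorers have less room to gain and widen the baseline spread. The documents do not support this:
- Headroom at 11 of 20 is 9 items, still more than the largest assumed mean gain (8.0 − 3.0 = 5.0).
- The result of a gain-score calculation depends on what is held fixed. Take 30 per arm, the 1.5-point home difference, and a pre-test SD rising from 1.93 to 2.81 (the latter from an assumed Normal(4.5, 3.5) limited to 0–11). Holding the pre-post slope at 1.44 and the residual SD at 1.74, power falls from .84 to .76. The implied correlation then drifts from .85 to .92 and the post-test SD from 3.28 to 4.40, against the plan's .90 and 4.0.
- Holding the plan's values instead, gain SD = √(4.0² + s² − 2 × .90 × 4.0 × s). This is 2.41 at s = 1.93 and 1.91 at s = 2.81, and power rises from .66 to .85.

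**Conclusion.** The contradiction stands: below 60% in the criteria, against a cap of 7 of 20 tied to a 40% criterion that is not in the list and is written with the wrong sign. The production powers and the 0.35-logit or 2-raw-point difference were computed for an entry rule other than the one in the criteria. Even with the percentages aligned, a hard cap would not follow, because entry is decided on a different, 10-item probe and a child's 20-item score can exceed either ceiling.

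The size is small if the plan's pre-test distribution holds. It could be material, up or down, if the wider rule raises the pre-test mean or SD. The documents cannot settle which, so it would be wrong to read this point as showing that the trial is underpowered. The randomisation and the planned models are unaffected.

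**What to change.** - Reconcile the eligibility list and the power section on one entry percentage. Which is right is for the sponsor to state; this review does not prejudge it.
- Correct >40% so that it reads as a ceiling, and say which probe it applies to.
- Rerun the existing simulation with a pre-test distribution that matches the entry rule in force, without a hard cap borrowed from the 10-item screen. If a blinded, pooled pre-test mean and SD are available from children already enrolled, use them. State how out-of-range draws are handled and whether raw or logit gains are held constant.
- Restate the powers and the detectable difference, in the Aim 1 text too. Check whether the Aim 2 dose simulation, which adds gains to pre-test scores, used the same cap.

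The cost is one simulation rerun and figures that may differ from those now stated. Enrolment does not change.

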We will also use generalized additive mixed models (GAMMs) to model longitudinal patterns in eyetracking data (i.e., looks to the agent) to examine and visualize timing of stimulus effects and changes in focus at key points during and after presentation of the prompt. GAMMs model fixations as an intensive time series (Cho et al., 2018, 2022) and allow identification of key points of separation. Moreover, the GAMMs models do not require prespecification of windows of time, providing more flexibility and sensitivity when modeling differences in eyetracking over time and between groups. The specification of the GAMMs models will mirror the GLMM equations below, except that smoothing functions will be used for an additional TIME predictor to fit a spline regression for each time series.

Aim 1. Determine the relative differences in the efficacy of illustrated syntax stories and recast therapy when treatment is dose controlled and delivered by highly trained SLPs in the laboratory.

We will first confirm that we achieved control of dose in the two in-lab conditions. We will carry out an unpaired two-tailed t-test comparing the estimated dose delivered for each condition. We anticipate that the two conditions will not differ and that the distributions will show high degrees of overlap ($p>.5$, $d<.3$).

To test the key question in Aim 1, we will compare the relative effect of treatment condition by testing for differences between the treatment effect estimates of stories in the lab and recasts in the lab conditions.

Well-matched groups at pretest will be evident if the two conditions do not differ at pre-test. If one treatment condition is more effective than the other, this should be evidenced by an interaction between test point and treatment contrast effects that are significant at the p<.05 level; if, as we hypothesize, the two conditions are equally effective there will be no significant interaction between test point and treatment. We are powered to detect an effect size difference of .35 (2 raw score points) or larger on production.

$$\begin{aligned} \text{Likelihood of a Correct Production} &= \text{TestPoint} * \text{TreatmentCondition} \\ &\quad + (1|\text{item}) + (\text{clause type} |\text{subject}) \\ \text{Structural Sensitivity} &= \text{TestPoint} * \text{TreatmentCondition} \\ &\quad + (\text{clause type} |\text{subject}) \end{aligned}$$

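### The blanket statement that all unlisted treatment contrasts have power below 80% is false for home stories vs lab recasts and doubtful for Aim 1's lab contrast, which gets no power figure of its own

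*Protocol*

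**What the plan says.** All references are to the Protocol.

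- **Power Analysis for Production, assumed effects.** The standardized effects are 1.0 for stories at home, 0.4 for parent recasts, 1.2 for stories in the lab and 2.0 for lab recasts.
- **Same section, listed contrasts.** Power is .75 for stories at home vs parent recasts and .99 for parent recasts vs lab recasts. For the third listed contrast it is .90; after the decimal point the text reads "90 to detect differences in parent recasts and syntax stories in the lab effects".
- **Same section, the rest.** "Other contrasts (e.g., syntax stories at home vs. syntax stories in the lab) have power less than 80% if the expected effect sizes hold true". A bracket repeats the effects 1.0 and 1.2. The sentence then sets the difference needed for 80% power at 0.35 logits, equated with 2 raw points.
- **Same section, opening paragraph.** Power for the narrower aim-specific models is to be inferred from the contrast figures that follow.
- **Analytic Approach, Aim 1.** The key test compares stories in the lab with recasts in the lab through a test point by treatment interaction, judged "significant at the p<.05 level". The section adds: "We are powered to detect an effect size difference of .35 (2 raw score points) or larger on production".

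**The concern.** Four arms give six pairwise contrasts. Once three are listed, the word for the remainder takes in home vs lab stories, lab stories vs lab recasts, and home stories vs lab recasts. The first is tiny. The other two are as large as, or larger than, a listed contrast with power .90, at least in the effect-size and raw units in which the protocol states its assumptions.

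One of these is the comparison on which Aim 1 turns. Aim 1 expects no interaction, so the weight of a null result depends on the power of this contrast. The reader is told to infer it from the listed figures, but none of them is for this contrast, and the only sentence that reaches it says below 80%.

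**Working it through.** **Inputs** (Power Analysis for Production): pretest mean 3.0, SD 2.5; 20 items per test; treated posttest mean/SD of 5.5/4.0 (stories at home, HS), 4.0/4.0 (parent recasts, PR), 6.0/3.5 (stories in lab, LS) and 8.0/3.5 (lab recasts, LR). Level .05; sidedness is not stated for the interaction test, so two-sided is assumed.

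**Step 1: reproduce the effect sizes.** ES = (M − 3.0)/2.5 gives HS 1.0, PR 0.4, LS 1.2, LR 2.0, as stated.

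**Step 2: size each contrast.** The logit gap uses ln[p/(1 − p)] with p = M/20: HS −0.969, PR −1.386, LS −0.847, LR −0.405.

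| Contrast | ES gap | Raw gap | Logit gap | SDs | Stated power |
|---|---|---|---|---|---|
| HS vs PR | 0.6 | 1.5 | 0.417 | 4.0/4.0 | .75 |
| PR vs LS | 0.8 | 2.0 | 0.539 | 4.0/3.5 | .90 |
| PR vs LR | 1.6 | 4.0 | 0.981 | 4.0/3.5 | .99 |
| HS vs LS | 0.2 | 0.5 | 0.122 | 4.0/3.5 | below .80 |
| LS vs LR (Aim 1) | 0.8 | 2.0 | 0.442 | 3.5/3.5 | below .80 |
| HS vs LR | 1.0 | 2.5 | 0.564 | 4.0/3.5 | below .80 |

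HS vs LR exceeds PR vs LS in all three units with the same pair of SDs. It also exceeds both forms of the 80% threshold (0.35 logits, 2 points). LS vs LR equals PR vs LS in ES and raw units with one smaller SD, and exceeds 0.35 logits, but its logit gap is smaller than that of PR vs LS.

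**Step 3: scale from the listed powers.** Power ≈ Φ(gap/SE − 1.96), so SE = gap/(z_power + 1.96). The denominator is 2.634 for .75 and 3.242 for .90.

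- Raw SE: 1.5/2.634 = 0.569 or 2.0/3.242 = 0.617.
- Logit SE: 0.417/2.634 = 0.158 or 0.539/3.242 = 0.166.

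| Contrast | Raw/ES scale | Logit of nominal means |
|---|---|---|
| LS vs LR | .90 to .94 | .76 to .80 |
| HS vs LR | .98 to .99 | .92 to .95 |

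The protocol's own logit threshold is more generous: 80% power at 0.35 logits gives SE = 0.35/2.802 = 0.125, and LS vs LR then has Φ(0.442/0.125 − 1.96), about .94.

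**Step 4: allow for the floor at zero.** The simulated posttests were floored at 0, which lifts the mean to MΦ(M/SD) + SDφ(M/SD), most of all for parent recasts (4.0 becomes 4.33). The logit gaps become 0.453 for PR vs LS, 0.354 for HS vs PR and 0.430 for LS vs LR. Scaled as in step 3, LS vs LR has about .87 to .89.

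**Step 5: direct calculation.** With 30 children per arm (120 in the simulation, equal allocation assumed) and the stated pre-post correlation of .90:

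| Method | PR vs LS (stated .90) | LS vs LR | HS vs LR |
|---|---|---|---|
| Gain in treated clause, closed form | .985 | .997 | .999 |
| Treated minus untreated gain, closed form | .945 | .972 | .993 |
| Same, simulated t-test | .82 to .87 | .90 to .94 | .96 to .97 |
| Reduced logistic mixed model, simulated | .75 to .77 | .78 to .81 | .93 to .95 |

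The simulations used 300 runs per setting and assumed a between-clause correlation of 0 or .5; the mixed model had no item effects. The stated .75 and .90 were not reproduced. A fuller fixed-effects coding gave far lower values (.15 to .16, .15 and .37 to .39 for the three columns), so absolute power depends on coding that the protocol does not give. The order is stable: HS vs LR has more power than PR vs LS throughout, and LS vs LR has at least as much, within simulation error.

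**The case against.** Three counter-arguments deserve weight.

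1. **Scale.** Production is analyzed with a logit link and power came from a logistic mixed model. On the logit of the nominal means the .90 contrast (0.539) is larger than Aim 1's (0.442), and scaled power of .76 to .80 is compatible with a figure below 80%. This stands. A reader might infer that the .90 contrast is no larger than Aim 1's on any scale; the documents support that only in ES and raw units. The argument does nothing for home stories vs lab recasts.

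2. **Wording.** The sentence names one example, and its bracket fits only that example, so it may be loose drafting rather than a wrong calculation. That is plausible. But if so, Aim 1's contrast has no power figure at all, although the reader is told to infer one.

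3. **No contradiction between sections.** A reader might infer that the Aim 1 section claims adequate power while the power section denies it. The documents do not support that: both give the same detectable difference, 0.35 or 2 raw points, and the planned lab gap of 2.0 points lies on that boundary. Nor is a null Aim 1 result uninterpretable, since a detectable difference is stated and a treated vs untreated comparison follows a null interaction.

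It is also fair to say that the one clearly false placement concerns a contrast that neither aim tests.

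**Conclusion.** The concern holds in limited form. As written, the statement is false for home stories vs lab recasts: this contrast exceeds the .90 contrast on every scale and has about .92 to .99 power when scaled from the protocol's own figures. For Aim 1's lab stories vs lab recasts, it is inconsistent with the .90 on the ES and raw scales and with the 0.35-logit threshold; on the logit of the nominal means it is doubtful but not shown false. It is right for home vs lab stories.

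This rests on the stated powers being correct, a two-sided .05 test, and a roughly common standard error across contrasts. It is an argument from internal consistency. Failure to reproduce .75 and .90 is not evidence of error, because item variance, between-clause correlation and fixed-effects coding are not given. Sample size and planned analyses are unaffected; what changes is the power that can be claimed for the Aim 1 comparison.

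**What to change.** - In Power Analysis for Production, replace the blanket sentence with the simulated power for all six contrasts. Keep the below-80% remark for stories at home vs stories in the lab, and for any other contrast that the simulation actually puts there.
- State the lab stories vs lab recasts figure explicitly, both there and in the Aim 1 paragraph of the Analytic Approach, on one named scale (logit, raw points or standardized effect).
- While doing so, reconcile the 80% threshold of 2 raw points with the .90 given to a contrast of exactly 2 points.

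The cost is reading three more contrasts from the existing simulation and rewriting a few sentences. No design change or new data are needed.
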